# 9.3.1. Part A Monotherapy

The number of patients to be enrolled in the study will depend upon the observed safety profile, which will determine the number of patients at each dose level and the number of dose levels explored.

At least 9 patients will be treated at the dose declared as the MTD. If MTD was not reached by definition of safety criteria, this statement will apply for highest tested dose level.

The sample size using the mTPI approach cannot be determined in advance. It is estimated the number of DLT evaluable patients to be enrolled in the dose escalation stage will allow a reliable and accurate estimate of the MTD.

The exact sample size of the mTPI design in Part A1 cannot be pre specified in advance because it is a dynamic feature of the design. The maximum sample size after which the Part A1 will be stopped and MTD declared is 58 patients. Also, a minimum of 9 patients is required to establish the MTD. The actual sample size of Part A1 will depend on the underlying dose toxicity profile and variability in actual data realization.

As for the number of patients treated at each dose, it is expected that the typical number will be 2 to 4 patients for the doses actually studied. For the dose declared as MTD at the end of Part A1, this number will be at least 9 patients.

The planned sample size for Part A2 expansion cohort is up to 40 evaluable patients. An evaluable patient will have both a baseline and on-treatment tumor biopsy. Aggregate toxicity will be monitored for patients in Part A2. DLT will continue to be assessed in Part A2, and data acquired in Part A1 dose-escalation phase and Part A2 dose expansion phase will be combined to assess the toxicity (as suggested by Lasonos and O'Quigley, 2014). In the event the observed toxicity exceeds 30%, a revised MTD may be recommended.

Although the A2 sample size is not based on any statistical considerations, the study would have 69% power to assess an overall response rate of 10% with 20 patients assuming the overall response rate of current therapy is 2%,  $^{96}$  using a one-sample test under a two-sided  $\alpha$  level of 0.1. The study would have about 93% power if the true response rate is 20%. A table of 90% confidence intervals based on observed number of responders is provided below for reference:

Table 7. 90% Confidence Intervals of Overall Response I	Rate
---	------

	N=20	90% Confidence Interval		
Observed Responders	ORR	Lower Limit	Upper Limit	
0*	0	0	5.6%	
1	5%	0	15.5%	
2	10%	0	23.5%	
4	20%	2.8%	37.2%	
6	30%	10.6%	49.4%	
8	40%	19.5%	60.5%	

\*: with 0.005 continuity correction for confidence interval calculation

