# 9.3. Sample Size Determination

A maximum of approximately 210 patients are expected to be enrolled into the study. The total sample size is not based on formal hypothesis testing considerations.

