4. HYPOTHESES AND DECISION RULES

4.1. Statistical Hypotheses

This clinical trial implements a Bayesian procedure to determine the MTD. No classical hypothesis testing will be done. Decisions will be based on Bayesian posterior probabilities arising from a full hierarchical probability model.

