7. STATISTICAL METHODOLOGY AND STATISTICAL ANALYSES

7.1. Statistical Methods

The statistical summaries are non-inferential. The data are summarized by cohort defined by the initial dose of the study drug.

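### Part A2 power at a 10% response rate is stated as 69%; that is a normal-approximation figure, and the rule it implies (2 or more responders of 20) has exact power 60.8%

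*Protocol*

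**What the plan says.** Protocol section 9.3.1 (Part A Monotherapy) states that "the study would have 69% power to assess an overall response rate of 10% with 20 patients". The reference rate for current therapy is 2%, and the calculation is described as "using a one-sample test under a two-sided" alpha of 0.1. It then adds: "The study would have about 93% power if the true response rate is 20" (percent). Twenty patients is one arm of Part A2. No test statistic is named and no number of responders is given as the threshold. Table 7 follows with 90% confidence intervals for selected responder counts out of 20.

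The same sentence opens with a qualification: "Although the A2 sample size is not based on any statistical considerations". Section 9.3 says of the whole study: "The total sample size is not based on formal hypothesis testing considerations". In the SAP, section 4.1 states "No classical hypothesis testing will be done" and section 7.1 states "The statistical summaries are non-inferential".

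**The concern.** At a 2% response rate, 20 patients yield 0.4 responders on average. A normal approximation to the binomial is unreliable there, and power moves in large steps as the cut-off changes by one responder. A power quoted without a test or a cut-off cannot be checked directly, and 69% does not correspond to any whole-number cut-off at n = 20.

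These two sentences are the protocol's only power statement for 20 Part A2 patients. A reader would take the chance of detecting a 10% response rate as roughly 7 in 10. If the rule actually available gives roughly 6 in 10, the protocol credits the cohort with sensitivity that it lacks.

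**Working it through.** **Inputs (all from Protocol 9.3.1).** n = 20; reference rate p0 = 0.02; alternatives p1 = 0.10 and 0.20; two-sided alpha 0.1, so 0.05 per tail and z = 1.645.

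**Step 1: reproduce the stated powers.** The null standard error is √(0.02 × 0.98 / 20) = 0.0313. A two-sided z-test rejects outside 0.02 ± 1.645 × 0.0313 = 0.02 ± 0.0515:

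- upper bound 0.0715, which is 1.43 responders;
- lower bound −0.0315, which is −0.63 responders.

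Power is Φ((p1 − 0.0715)/SE1) + Φ((−0.0315 − p1)/SE1), with SE1 = √(p1(1 − p1)/20).

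- p1 = 0.10 (SE1 = 0.0671): 0.6646 + 0.0250 = 0.6896, against the stated 69%.
- p1 = 0.20 (SE1 = 0.0894): 0.9246 + 0.0048 = 0.9294, against the stated 93%.

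Both figures come out to the rounding shown. The upper tail alone gives 66.5% at 10%, so the lower tail is needed to reach 69%.

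Table 7 also points to normal approximations. Its limits equal p̂ ± (1.645 × √(p̂(1 − p̂)/20) + 0.025), where 0.025 = 1/(2 × 20). The upper limit is 15.5% at 1 responder and 23.5% at 2, and the lower limit is 2.8% at 4.

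**Step 2: what the test can do with whole responders.** The lower region requires a negative response rate, so its 2.5 points at p1 = 0.10 cannot occur. In the upper region, z = (x/20 − 0.02)/0.0313 is 0.96 at x = 1 and 2.56 at x = 2. The test therefore rejects at 2 or more responders of 20 and at no other outcome.

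**Step 3: exact probabilities.** For 2 or more responders, P = 1 − (1 − p)^20 − 20p(1 − p)^19. At p = 0.10 this is 1 − 0.1216 − 0.2702 = 0.6083. Other cut-offs, also from the binomial distribution:

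| Responders needed | ORR 2% (type I error) | ORR 10% | ORR 20% |
|---|---|---|---|
| 1 or more | 33.2% | 87.8% | 98.8% |
| 2 or more | 6.0% | 60.8% | 93.1% |
| 3 or more | 0.7% | 32.3% | 79.4% |
| 4 or more | 0.06% | 13.3% | 58.9% |

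The gap at 10% is 69 − 60.8 = 8.2 points. About 2.5 points are the impossible lower tail, and the remaining 5.6 or so (66.5 − 60.8, before rounding) come from the continuous approximation. At 20% the stated 93% agrees with the exact 93.1%. No row gives 69% at 10%.

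**The case against.** The strongest reply is that nothing was miscalculated. A standard two-sided formula applied to the stated inputs gives 69% and 93%, so the criticism is of the method rather than the arithmetic. It is also true that the protocol does not state the normal-approximation origin and does not name 2 or more of 20 as a rule. Other readings exist. Holding each exact tail to 5% requires 3 or more responders, and the first row of Table 7 with a lower limit above 2% is 4 of 20. Finally, the documents describe the sample size as non-statistical, plan no test against 2%, and make anti-tumor activity a secondary objective. The response-based enrollment rule applies to Part B2, not Part A2.

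Some of this stands. The origin is an inference, though a single formula matches both published figures without adjustment. The 6.0% type I error is within the stated 10%, so it is not itself a fault. The low impact is real.

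The reply does not rescue the figure. Power describes what the design will do, and no cut-off at n = 20 gives 69% at a 10% rate. The rules requiring 3 or 4 responders make the overstatement larger, and neither gives the stated 93% at 20%. The rule of 2 or more is the one the z-test applies, and it agrees with that second figure.

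**Conclusion.** The 69% is wrong as a statement of the power available. Under the rule implied by the test that reproduces both stated figures, exact power at a 10% response rate is 60.8%, about 8 points lower, with exact type I error 6.0%. The figure of about 93% at a 20% rate is correct for that rule.

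This rests on 20 evaluable patients in an arm, a 2% reference rate, and the two-sided normal-approximation test as the source. If an exact test with at most 5% in each tail was meant, the cut-off is 3 or more, and power is 32.3% at 10% and 79.4% at 20%.

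The point is minor. No sample size, planned analysis or Part A2 decision rule depends on the figure.

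**What to change.** Replace the two power sentences in Protocol 9.3.1 with exact operating characteristics for a named cut-off. For example: *with 20 patients per arm, the probability of observing 2 or more responders is 6.0%, 61% and 93% if the true response rate is 2%, 10% and 20%.* If a stricter cut-off of 3 or more is preferred, the corresponding figures are 0.7%, 32% and 79%. Alternatively, delete the power claim, which would fit the SAP's position that no classical test is planned.

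The cost is protocol wording only. No patients are added and no analysis changes.

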overall survival of 10.7 vs 7.9 months, PFS 5.5 vs 2.8 months, ORR of 2% vs 1%, disease control rate of 43% vs 32% compared to placebo.  Recently, regorafenib, another multikinase inhibitor, was approved for HCC patients who have progressed during sorafenib treatment. Regorafenib improved overall survival with a median survival of 10.6 months vs 7.8 months for placebo, PFS 3.1 vs 1.5 months, ORR of 11% vs 4%, disease control rate of 49% vs 23%. 105 Additionally, a Phase II study evaluating lenvatinib, a multi-tyrosine kinase receptor inhibitor, for HCC treatment showed promising outcomes, with median survival of 18.7 months, TTP of 7.4 months, an ORR of 37%, and a disease control rate of 78%. 106 There is evidence to suggest that HCC is amenable to immunotherapy. Firstly, HCC tumor recurrence has been linked to immunosuppression. Secondly, HCC patients treated with autologous lymphocytes activated in vitro with recombinant interleukin-2 and antibody to CD3 had significantly improved recurrence-free survival and disease-specific survival. Thirdly, CD4+ regulatory T cells and immunosuppressive T regulatory cells (Tregs) that may suppress T cell responses have been identified in tumors of HCC patients, and it has been demonstrated that engagement of another T cell co-stimulatory receptor GITR can reverse the suppressive effect of Tregs. 55,56 It should however be noted that the liver has a unique intrinsic tolerogenic and intra-hepatic immunosuppressive environment, with mechanisms that preferentially inactivate T cells, as well as mechanisms that increase T cell tolerance, and apoptosis. As such, for the limited number of immunotherapeutic trials completed to date involving therapeutic vaccination and cell therapy strategies, only modest results have been observed. There are data that suggest that immune checkpoint inhibition with anti-PD1 may have anti-tumor efficacy in HCC. In the Checkmate 040 Phase 1/2 study, patients with advanced or metastatic HCC were treated with nivolumab. Objective responses occurred in 16% and CR in 1% of 214 patients, and responses were seen regardless of PD-L1 status, prior sorafenib treatment, or hepatitis C virus (HCV) or hepatitis B virus (HBV) infection. 98

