# 4.1.1. Part A Monotherapy

- 1. Part A1 only: Patients with histological or cytological diagnosis of HNSCC, HCC, melanoma, or clear cell RCC who progressed on or are intolerant to standard therapy, for which no standard therapy is available or who decline standard therapy.
- 2. Part A2 only: Patients with histological or cytological diagnosis of advanced/metastatic HCC who are treatment naïve and have declined standard of care, or have had at least 1 prior line of systemic therapy. Prior anti-PD-L1/PD-1 therapy is allowed.
- 3. Patients must have at least one measurable lesion as defined by RECIST version 1.1, be willing to undergo the mandatory biopsies and there is no excessive risk from biopsy as judged by the Investigator.
- 4. Adults (men and women) age  $\geq 18$  years (for Japan only:  $\geq 20$  years of age).
- 5. Eastern Cooperative Oncology Group (ECOG) Performance Status (PS) 0 or 1.
- 6. Adequate Bone Marrow Function, including:
  - ANC  $\ge 1,500/\text{mm}^3 \text{ or } \ge 1.5 \times 10^9/\text{L}.$
  - ANC for HCC only  $\ge 1,000/\text{mm}^3$  or  $1.0 \times 10^9/\text{L}$ .
  - Platelets  $\ge 100,000/\text{mm}^3$  or  $\ge 100 \times 10^9/\text{L}$ .

- Platelets for HCC only: ≥60,000/mm^3.
- Hemoglobin ≥9 g/dL. Limited transfusions to reach this value are allowed, after discussion with sponsor's medical monitor. There should not be a chronic need for transfusions in the recent (approximately 3 month) past.
- 7. Adequate Renal Function, including:
  - Serum creatinine ≤1.5 x upper limit of normal (ULN) or estimated creatinine clearance ≥60 ml/min as calculated using the method standard for the institution. If an estimated creatinine clearance is believed to be inaccurate for a patient, 24 hr urine collection with actual assessment of creatinine clearance is allowed.
- 8. Adequate Liver Function (all patients, except HCC, see Inclusion Criteria 9), including:
  - Total serum bilirubin  $\leq 1.5$  x ULN unless the patient has documented Gilbert syndrome.
  - Aspartate and alanine aminotransferase (AST & ALT)  $\leq$  2.5 x ULN;  $\leq$  5.0 x ULN if there is liver involvement secondary to tumor.
- 9. Inclusion for HCC patients only:
  - Child-Pugh Class A or B with a score of 7 (see Appendix 3) and no prior history of hepatic encephalopathy.
  - Serum bilirubin ≤3 mg/dL.
  - Serum Albumin ≥2.8 g/dL.
  - AST and ALT  $\leq$  5.0 x ULN.

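### The Part A2 power figures take the sorafenib response rate of 2% as current therapy, although the protocol reports 11% for regorafenib and 16% for nivolumab

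*Protocol*

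**What the plan says.** Section 9.3.1 of the protocol introduces the power statement with a disclaimer, "Although the A2 sample size is not based on any statistical considerations". Its main claim is that "the study would have 69% power to assess an overall response rate of 10% with 20 patients". The reference rate behind this claim is a stated assumption, in the words "assuming the overall response rate of current therapy is 2"%. The calculation is for a one-sample, two-sided test with α set at 0.1, and a second figure of about 93% is given for a true rate of 20%. The citation attached to the 2% is reference 96, the phase 3 trial of sorafenib in advanced HCC.

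Section 1.2.5.3 confirms 2% as the ORR with sorafenib (1% with placebo). For regorafenib, described there as approved for patients who progressed on sorafenib, it gives "PFS 3.1 vs 1.5 months, ORR of 11% vs 4%, disease control rate of 49% vs 23"%. For nivolumab it says "Objective responses occurred in 16% and CR in 1% of 214 patients". The Document History cites FDA approval of nivolumab in HCC among the rationales for Amendment 6.

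Inclusion criterion 2 in Section 4.1.1 admits two kinds of Part A2 patient: those with no earlier treatment who refused standard care, "or have had at least 1 prior line of systemic therapy. Prior anti-PD-L1/PD-1 therapy is allowed".

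**The concern.** The power sentence describes 2% as the rate for current therapy in general. On the protocol's own account, 2% belongs to one first-line drug, and two later agents have rates five and eight times as high (11/2 = 5.5, 16/2 = 8). Eligibility was updated to reflect those agents, but the reference rate was not.

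What is at stake is how the A2 response data are read. Establishing the recommended phase 2 dose is a primary objective of Part A2, anti-tumour activity is a secondary one, and SAP Section 7.2.1 links the choice of dose to clinical activity as judged by response rate. A reader who takes 69% and 93% at face value will believe that 20 patients per arm can separate this drug from what HCC patients can now receive. The figures speak only to a comparison with sorafenib.

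**Working it through.** **Inputs.** n = 20 per arm, two-sided α = 0.10, reference rate p0 = 2%, true rates p1 = 10% and 20% (Section 9.3.1). Other reference rates, from Section 1.2.5.3: 4% (placebo after sorafenib), 11% (regorafenib), 16% (nivolumab). The same section reports 37% for lenvatinib, but as a phase II result and not as an approved therapy, so I leave it out.

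**Formula.** One-sample normal-approximation test with null variance in the cut-offs and alternative variance in the power:

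- Upper and lower cut-offs: U, L = p0 ± 1.645 × √[p0(1 − p0)/20]
- Power = 1 − Φ((U − p1)/s1) + Φ((L − p1)/s1), where s1 = √[p1(1 − p1)/20]

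**Step 1: reproduce the stated figures (p0 = 2%).** √(0.02 × 0.98/20) = 0.0313, so U = 0.0715 and L = −0.0315.

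- p1 = 10%: s1 = 0.0671. Upper tail 1 − Φ(−0.425) = 66.5%; lower tail Φ(−1.960) = 2.5%; total 69.0%.
- p1 = 20%: s1 = 0.0894. Upper tail 1 − Φ(−1.437) = 92.5%; lower tail Φ(−2.588) = 0.5%; total 92.9%.

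Both match the protocol. The 69% includes a lower-tail contribution whose cut-off is a negative response rate and so cannot occur. That is a small side point.

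**Step 2: change only the reference rate.** For example, with p0 = 11%, √(0.11 × 0.89/20) = 0.0700 and U = 0.2251. At p1 = 20% the upper tail is 1 − Φ(0.280) = 39.0% and the lower tail is 1.1%, total about 40%.

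| Reference rate | True ORR 10% | 20% | 30% | 40% |
|---|---|---|---|---|
| 2% (sorafenib) | 69% | 93% | 99% | >99% |
| 4% (placebo after sorafenib) | 45% | 84% | 97% | >99% |
| 11% (regorafenib) | below reference | 40% | 77% | 94% |
| 16% (nivolumab) | below reference | 17% | 52% | 83% |

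At a true ORR of 10%, the chance of rejecting upwards is 3.1% against 11% and 0.2% against 16%.

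**Step 3: exact binomial check, at most 5% in the upper tail.** Against 11% the cut is 6 of 20 (tail 1.75%), with power 19.6% at a true ORR of 20% and 58% at 30%. Against 16% the cut is 7 of 20 (tail 3.0%), with power 8.7% and 39%. Exact power is lower against 2% as well: the cut is 3 of 20 (tail 0.7%), with power 32% at a true 10% and 79% at 20%.

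**The case against.** The strongest reply is that nothing depends on the sentence. It is conditional on its stated assumption, it opens by saying that the A2 sample size has no statistical basis, and Section 9.3 says the same of the total. SAP Section 4.1 rules out classical hypothesis testing, and SAP Section 7.1 calls the summaries non-inferential. All of this stands, and it limits the point to the accuracy of a published design statement.

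The second reply concerns the population. The 2% is still the protocol's sorafenib figure for the untreated patients whom A2 also admits. The 11% applies after sorafenib. The 16% cannot serve for patients already given PD-1/PD-L1 therapy, and neither document gives a rate for them. This stands too. It means that neither 11% nor 16% is the right replacement, and equally that 2% should not stand for everyone.

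Third, Table 7 already shows the precision without any benchmark: 6 of 20 has a lower limit of 10.6%, which does not exclude 11%, and 8 of 20 has 19.5%, which excludes both newer rates. A careful reader can work this out, but the power sentence beside the table points the other way.

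Three stronger readings are tempting, and the documents do not support them.

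- *The 69% and 93% are miscalculated.* They are not (Step 1).
- *Two responders in 20 would be declared a success, which a drug no better than regorafenib or nivolumab would usually achieve.* The 7.15% cut-off does correspond to 2 of 20, and that count has probability 66% at a true 11% and 85% at 16%. But no rule in either document calls 2 of 20 positive, and its Table 7 interval (0 to 23.5%) includes 2%. The lowest tabulated count that excludes 2% is 4 of 20, with probability 17% at a true 11% and 40% at 16%.
- *Twenty patients can show nothing over 11% to 16% unless the true ORR is about 35% to 40%.* By the protocol's own method, power against 11% is 77% at a true ORR of 30%, which is above the 69% that the protocol quotes.

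**Conclusion.** The point holds as a mislabelled benchmark. Section 9.3.1 presents a sorafenib rate as current therapy while Section 1.2.5.3 reports 11% and 16% for later agents. The computed power is right at 2%. At a true ORR of 20% it falls from 93% to 40% against 11% and to 17% against 16%, and the 69% at a true 10% has no meaning as power to improve on either agent.

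This rests on the protocol's own test (normal approximation, both tails counted, n = 20, α = 0.10) and on taking the Section 1.2.5.3 rates as reference points, although they come from different populations. A reader might infer that Part A2 is too small or that a planned analysis is invalid. Neither follows, because no comparison with a historical rate is planned and the sample size was not derived from one.

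**What to change.** In Section 9.3.1:

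- Label 2% as the sorafenib rate.
- Restate power by the same method against each reference: 2% (69% at a true ORR of 10%, 93% at 20%), 4% (45%, 84%), 11% (40% at 20%, 77% at 30%, 94% at 40%) and 16% (17%, 52%, 83% at the same three rates).
- Note that a true ORR of 10% is below the 11% and 16% references, and that exact-test power is lower (58% against 11% and 39% against 16%, both at a true ORR of 30%).
- State that the figures are illustrative, that no single benchmark fits a population mixing untreated and pretreated patients, and that the documents give no rate for patients pretreated with PD-1/PD-L1 agents.

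This is a wording change. It needs no extra patients and no new analysis. Its only cost is a less favourable stated power.

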7.1.3. Analyses for Binary endpoints

Binary data will be summarized using number of unique patient incidence, and confidence interval for binomial proportions may be presented

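### The Part A2 power figures imply a cut-off of 2 responders in 20, but the 90% interval printed below them excludes the 2% reference rate only from 4 in 20

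*Protocol*

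**What the plan says.** Protocol 9.3.1 first says that the A2 sample size has no statistical basis. It then says that "the study would have 69% power to assess an overall response rate of 10% with 20 patients". The comparison rate is 2%, taken as the response rate on existing treatment. The test is described only as one-sample, at a two-sided alpha of 0.1, and its statistic is not named. For the higher rate the protocol says: "The study would have about 93% power if the true response rate is 20" per cent.

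The paragraph continues: "A table of 90% confidence intervals based on observed number of responders is provided below for reference". For N=20, Table 7 prints 0 to 15.5% at 1 responder, 0 to 23.5% at 2, 2.8% to 37.2% at 4, 10.6% to 49.4% at 6 and 19.5% to 60.5% at 8. There is no row for 3 responders, and the interval method is not named apart from a footnote on the zero row.

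For reporting, Protocol 9.4 promises confidence intervals with the response rates but gives no method or level. SAP 4.1 says: "No classical hypothesis testing will be done". SAP 7.1.3 says that a "confidence interval for binomial proportions may be presented", again with no method or level. The SAP introduction states that the SAP supersedes the protocol's statistical considerations.

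**The concern.** A two-sided test at alpha 0.1 and a 90% interval are natural counterparts. A reader will expect the interval in Table 7 to exclude 2% whenever the test in the sentence above it rejects 2%. At 2 of 20 it does not: the printed interval starts at 0.

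The powered test will not be run, so any comparison with 2% can appear only through an interval. Someone told that an arm has 93% power at a true rate of 20% could then be shown an interval that often fails to exclude 2%. SAP 7.2.1 mentions response rate alongside tolerability when it describes the search for a dose, so the response summaries may carry some weight. They are planned as descriptive statistics only.

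**Working it through.** **Inputs (Protocol 9.3.1).** n = 20; reference rate p0 = 0.02; two-sided alpha 0.10, so z = 1.645; true rates p1 = 0.10 and 0.20; stated power 69% and about 93%.

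**Reproducing the power figures.** Use a z-test with the null variance and count both tails:

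- se0 = sqrt(0.02 × 0.98 / 20) = 0.0313. The test rejects above 0.02 + 1.645 × 0.0313 = 0.0715, or below −0.0315.
- p1 = 0.10: se1 = sqrt(0.10 × 0.90 / 20) = 0.0671. Upper tail 1 − Φ((0.0715 − 0.10)/0.0671) = 66.5%; lower tail Φ((−0.0315 − 0.10)/0.0671) = 2.5%; total 69.0%.
- p1 = 0.20: se1 = 0.0894. Upper tail 92.5%; lower tail 0.5%; total 92.9%.

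Both stated figures reproduce. The other versions tried do not match both (true rate 10% / 20%):

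| Calculation | 10% | 20% |
|---|---|---|
| z-test, upper tail only | 66.5% | 92.5% |
| z-test, continuity-corrected | 52.1% | 87.6% |
| z-test, variance under the alternative | 32.6% | 64.3% |
| z-test, one-sided 0.10 | 72.4% | 94.1% |
| Arcsine | 48.6% | 89.1% |
| Exact binomial, 2 or more of 20 | 60.8% | 93.1% |

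**Cut-off of that test.** An observed 1 of 20 (5%) is below 7.15%, and 2 of 20 (10%) is above it. The rule is therefore 2 or more responders. Its exact power is P(X ≥ 2) = 60.8% at 10% and 93.1% at 20%. The 69% is too high partly because 2.5 points of it come from observed rates below −3.1%, which cannot occur.

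**Reproducing Table 7.** Use a Wald interval with a 1/(2n) = 0.025 correction, cut off at 0: p ± (1.645 × sqrt(p(1 − p)/20) + 0.025).

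| Responders | Computed | Printed |
|---|---|---|
| 1 | 0 (−5.5%) to 15.5% | 0 to 15.5% |
| 2 | 0 (−3.5%) to 23.5% | 0 to 23.5% |
| 3 | 0 (−0.6%) to 30.6% | no row |
| 4 | 2.8% to 37.2% | 2.8% to 37.2% |
| 6 | 10.6% to 49.4% | 10.6% to 49.4% |
| 8 | 19.5% to 60.5% | 19.5% to 60.5% |

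The first count whose lower limit exceeds 2% is 4. Dropping the correction does not change this, because 3 of 20 then gives 1.9%.

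**Exact chance that a 90% interval excludes 2%, by method.**

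| Interval | Cut-off | True rate 10% | True rate 20% | True rate 2% |
|---|---|---|---|---|
| Wilson score | 2 or more (lower limit 3.4% at 2/20) | 60.8% | 93.1% | 6.0% |
| Clopper-Pearson | 3 or more (1.8% at 2/20, 4.2% at 3/20) | 32.3% | 79.4% | 0.7% |
| Table 7 formula | 4 or more | 13.3% | 58.9% | 0.06% |

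The like-for-like gap between the powered test and Table 7 is the chance of seeing exactly 2 or 3 responders. It is 60.8 − 13.3 = 47.5 points at a true rate of 10%, and 93.1 − 58.9 = 34.2 points at 20%.

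**The case against.** The strongest reply is that nothing was miscalculated. The two power figures are right for a test of the kind the sentence names, and the rows of Table 7 checked above are right for their formula. The sentence never claims to be the chance that the printed interval excludes 2%. The protocol disclaims a statistical basis for the A2 size and offers the table for reference. Response rate is secondary in A2, and SAP 7.1 calls the summaries non-inferential. Protocol 3.6 bases the recommended phase 2 dose on tolerability and pharmacodynamic effect and does not list response rate.

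Most of this stands and limits the point. A reader might infer that 2 or 3 responders would be declared a success, or that a planned analysis fails. The documents do not support that, because no A2 decision is tied to excluding 2%. A reader might also infer that the clinical study report will use the Table 7 interval. No document commits to it: Protocol 9.4 and SAP 7.1.3 name no method, and the SAP takes precedence.

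The reply does not remove the disagreement itself. Two adjacent statements about the same 20 patients and the same 2% benchmark use cut-offs two responders apart, and neither method is named. The 69% is also not the exact power of its own 2-of-20 rule.

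**Conclusion.** The inconsistency is real, with low-to-moderate severity. The stated 69% and 93% belong to a rule of 2 or more of 20, whose exact power is 61% and 93%. The interval printed beneath first excludes 2% at 4 of 20, with probability 13% and 59%. A Clopper-Pearson interval would give 32% and 79%.

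It is tempting to say that power falls from 69% to 13% at a true rate of 10%. That subtracts an exact figure from a normal approximation. The like-for-like drop is 61% to 13%, and the other 8 points or so are approximation error in the 69%.

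The conclusion rests on two things. First, the test and interval formulas are identified by reproducing the printed figures, because the protocol names neither. The cut-off of 4 relies on the reconstructed formula at 3 of 20, for which Table 7 has no row; the clash at 2 of 20 relies on the printed interval and the identified test. Second, the 13% and 59% apply only if response is judged by whether that interval excludes 2%, a rule that the plan does not set.

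**What to change.** Name one 90% binomial interval for response rate in SAP 7.1.3. Recompute every row of Table 7 with it and add a row for 3 responders. Restate the power in Protocol 9.3.1 as the exact probability that this interval excludes 2%, and give the cut-off. Any of three choices would be consistent:

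- **Wilson score**, which corresponds to the z-test behind the present figures. Rows: 0/20 0–11.9%; 1/20 1.1–19.6%; 2/20 3.4–26.2%; 3/20 6.2–32.2%; 4/20 9.3–37.8%; 6/20 16.4–48.4%; 8/20 24.2–58.1%. Cut-off 2 or more; power 61% (replacing 69%) and 93%. The cost is an upper-tail error of 6.0% at a true rate of 2%, slightly above the nominal 5%.
- **Clopper-Pearson.** Cut-off 3 or more; power 32% and 79%; error 0.7%.
- **Keep the Table 7 formula.** Cut-off 4 or more; power 13% and 59%.

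The cost is at most one recomputed table, restated power figures in the protocol and one line in the SAP. Nothing changes for patients, procedures or sample size.
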